2. TRIAL OBJECTIVES AND ENDPOINTS

2.1 MAIN OBJECTIVES, PRIMARY AND SECONDARY ENDPOINTS

2.1.1 Main objectives

The primary objective of this trial is:

Part A

- To determine the Maximum tolerated dose (MTD) and/or the recommended dose (RD) of BI 891065 monotherapy for further development in Asian patients with advanced solid tumours

Part B

- To determine the MTD and/or the RD of BI 891065 in combination with a fixed dose of BI 754091 at 240 mg for further development in Asian patients with advanced solid tumours

The definition of MTD and RD are as follows:

- MTD: the highest dose with less than 25% risk of the true DLT rate being equal or above 33% during the MTD evaluation period
- RD: RD is determined by SMC and it may be any dose which fulfil the escalation with overdose control (EWOC) criterion. The SMC may decide to declare a dose as RD without determining the MTD, in consideration of all available data including that from preceding trials.

The MTD will be determined based on the frequency of patients experiencing DLTs during the MTD evaluation period. The MTD evaluation period is defined as first treatment cycle (21 days). At the end of the dose escalation, the BLRM will be rerun using DLTs from all treatment cycles. This result as well as all available data will be used to define the RD.

The secondary objectives are:

Part A

- To document the safety and tolerability, and characterise pharmacokinetics (PK) of BI 891065 as monotherapy in Asian patients with advanced solid tumours

Part B

- To document the safety and tolerability, and characterise PK of the combination therapy of BI 891065 and BI 754091 in Asian patients with advanced solid tumours

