7. STATISTICAL METHODS AND DETERMINATION OF SAMPLE SIZE

7.1 STATISTICAL DESIGN – MODEL

7.1.1 Part A

The trial will be performed as an open-label trial. The objective of the design is to determine the MTD defined as the highest dose with less than 25% risk of the true DLT rate being above 0.33 (EWOC criterion). The dose-finding of Part A will be guided by a Bayesian 2-parameter logistic regression model with overdose control ([R13-4806](#); [R13-4803](#)).

The model is given as follows:

$$\text{logit}(\pi_d) = \log(\alpha) + \beta * \log(d/d^*),$$

where $\text{logit}(\pi) = \log(\pi/(1-\pi))$.

π_d represents the probability of having a DLT in the MTD evaluation period at dose d , $d^* = 200$ mg is the reference dose, allowing for the interpretation of α as the odds of a DLT at dose d^* , and $\theta = (\log(\alpha), \log(\beta))$ with $\alpha, \beta > 0$ is the parameter vector of the model.

The estimated probability of a DLT at each dose level from the model will be summarized using the following intervals:

Under toxicity: [0.00, 0.16)

Targeted toxicity: [0.16, 0.33)

Over toxicity: [0.33, 1.00]

The BLRM-recommended dose for the next cohort is the level with the highest posterior probability of the DLT rate falling in the target interval [0.16, 0.33) among the doses fulfilling EWOC. Applying the EWOC criterion, it should be unlikely (<25% posterior probability) that the DLT rate at that dose will exceed 0.33. However, the maximum allowable dose increment for the subsequent cohort will be no more than 100 %.

The MTD may be considered reached if one of the following criteria is fulfilled:

- The posterior probability of the true DLT rate in the target interval [0.16 – 0.33] of the MTD is above 0.5, OR
- At least 12 patients have been treated in the dose escalation phase of the trial, of which at least 6 at the MTD.

The SMC may decide stopping the dose escalation phase after the criterion for MTD is fulfilled. Further patients may be included to confirm this MTD estimate. If no DLT is observed at a dose of which the efficacy is considered sufficient, the SMC may decide to include an additional number of patients at this dose level and to declare this dose as the dose recommended for further testing.

The BLRM is set up for a fixed dosing schedule of once daily (q.d.) across dose levels of BI 891065. For the purpose of dose-toxicity modelling, a b.i.d. regimen will be converted in

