Proprietary confidential information © 2021 Boehringer Ingelheim International GmbH or one or more of its affiliated companies

metrics such as the probability of recommending a dose with true DLT rate in the target interval can be approximated via simulation. Table [10.4.1: 2](#) describes 6 assumed true dose-toxicity scenarios which were used to assess the operating characteristics of the model. These scenarios reflect a wide range of possible cases as follows:

- Scenario 1: aligned with prior means
- Scenario 2: high-toxicity scenario
- Scenario 3: low-toxicity scenario
- Scenario 4: non-logistic dose-toxicity scenario
- Scenario 5: low-toxicity followed by high-toxicity
- Scenario 6: super high-toxicity scenario

Table 10.4.1: 2 Assumed true dose-toxicity scenarios

Scenario		Dose (mg q.d.)					
		40*	50	100	200	400	600*
1: Prior	P(DLT)	NA	0.022	0.032	0.053	0.107	0.181
2: High Tox		NA	0.194	0.253	0.425	0.527	NA
3: Low Tox		NA	0.008	0.028	0.054	0.143	0.181
4: Non-Logistic		NA	0.032	0.098	0.268	0.467	NA
5: Low-High		NA	0.008	0.052	0.241	0.335	NA
6: Super High Tox		0.260	0.450	0.578	0.660	0.737	NA

* To allow the model to implement the above scenarios and to evaluate the operating characteristics, 40 mg and 600 mg doses were included even if they will not be tested in the trial.

For each of these scenarios, 1000 trials were simulated. Each cohort consisted of 3 patients and dose escalation complied with the following rules:

- Escalate to the dose which maximises the probability of the targeted toxicity region and satisfies the overdose criterion if it is $\leq 100\%$ increase from the current dose.
- If the recommended dose satisfying the overdose criterion is $> 100\%$ increase in dose, then escalate to the highest dose level which is $\leq 100\%$ increase from the current dose.

The MTD was considered reached if at least 6 patients have been evaluated at a dose level which is the model's recommendation for the next dose cohort and for which the posterior probability of targeted toxicity was at least 50%.

It was then assessed how often a dose was declared as MTD with true DLT rate in the under-, targeted or over-dose range.

Furthermore, the average, minimum and maximum number of patients per trial and the average number of DLTs per trial are reported. Results are shown in Table [10.4.1: 3](#).

Table 10.4.1: 3 Simulated operating characteristics

	% of trials declaring a MTD with true DLT rate in				# Patients	# DLTs

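### Section 7.1.1 lets the MTD be considered reached with no minimum number of patients at that dose, but the operating characteristics in 10.4.1 were simulated under a stricter rule

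*Protocol*

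**What the plan says.** Protocol 7.1.1 defines the MTD as the highest dose that satisfies overdose control (EWOC), that is, less than 25% posterior probability of a DLT rate above 0.33. It then gives two criteria for stopping, introduced by "The MTD may be considered reached if one of the following criteria is fulfilled":

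- Criterion 1: "The posterior probability of the true DLT rate in the target interval [0.16 – 0.33] of the MTD is above 0.5, OR"
- Criterion 2: "At least 12 patients have been treated in the dose escalation phase of the trial, of which at least 6 at the MTD"

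Only criterion 2 carries a patient count. Confirmation at the declared dose is optional: "Further patients may be included to confirm this MTD estimate". Protocol 2.1.1 and 3.1 and SAP 7.4.1 add no minimum.

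The simulations in protocol 10.4.1 used another rule: "The MTD was considered reached if at least 6 patients have been evaluated at a dose level", where that dose also had to be the model's next recommendation and to have a target probability of at least 50%. There the conditions are joined by *and*.

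Part B has the same mismatch between 7.1.2 (either criterion, with 9 patients in place of 12) and 10.4.2 (both conditions).

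**The concern.** Two things follow from the difference between *or* and *and*.

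First, Table 10.4.1: 3 is the evidence offered for how well the design finds the MTD, and it was produced under a stricter rule than the one written into the design section. A reader cannot take its percentages, patient numbers or DLT counts as properties of 7.1.1.

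Second, the model interpolates between doses, so criterion 1 can be met at a regimen nobody has received, from data at its neighbours. The natural candidate is 200 mg b.i.d. It has its own row in Table 7.1.1: 3 and enters the model as 300 mg q.d., a conversion that assumes steady-state peak concentration drives safety events. An MTD declared there without direct observation of that schedule would be a weaker result than the word MTD suggests.

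**Working it through.** **Model and inputs.** Section 7.1.1: logit(π_d) = log α + β·log(d/200). Table 7.1.1: 2: a two-component normal prior for (log α, log β), with means (−3.66, −0.28), SDs (1.20, 0.83), correlation −0.10 and weight 0.9; and means (−3, 0), SDs (2, 1), correlation 0 and weight 0.1. The posterior is prior × binomial likelihood, integrated on a grid. P(target) = P(0.16 ≤ π_d < 0.33) and P(OD) = P(π_d ≥ 0.33).

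**Reproducing the protocol's figures** (under / target / over, or P(OD) alone):

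| Quantity | Protocol | Grid |
|---|---|---|
| Prior, 200 mg b.i.d. (300-equivalent) | 0.873 / 0.086 / 0.041 | 0.872 / 0.086 / 0.042 |
| Prior, 400 mg | 0.813 / 0.115 / 0.072 | 0.810 / 0.115 / 0.075 |
| Table 10.4.1: 1, scenario 7, 200 mg | 0.520 / 0.340 / 0.140 | 0.519 / 0.336 / 0.145 |
| Table 10.4.1: 1, scenario 11, P(OD) at 400 mg | 0.413 | 0.412 |

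All 12 scenarios of Table 10.4.1: 1 agree within about 0.01.

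**Example at N = 12.** The steps follow the model, EWOC and the 100% escalation cap. The first result, 1/3 at 100 mg, is the Part A result reported in Table 7.1.2: 1.

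1. 100 mg 1/3: P(OD) at 400 mg is 0.182, but the cap limits the next dose to 200 mg.
2. 200 mg 0/3: 400 mg has P(target) 0.221 and P(OD) 0.081, so escalate.
3. 400 mg 1/3: P(target) 0.360 and P(OD) 0.127, so stay.
4. 400 mg 2/3, making 3/6: 400 mg has 0.457 and 0.402, so it fails EWOC. The 300-equivalent has 0.526 and 0.244. For 200 mg q.d. the values are about 0.46 and 0.10.

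Among the listed levels, 200 mg b.i.d. is now the highest dose under EWOC, and its P(target) exceeds 0.5. Criterion 1 is met with nobody on that regimen. Criterion 2 is not met there. The margin is thin: 0.25 − 0.244 = 0.006.

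**Example at N = 15.** Take the protocol's own scenario 11 (0/3, 0/3, 3/6) and add one cohort with 1 DLT at 200 mg, the dose that scenario recommends. This makes 0/3, 1/6 and 3/6. The 300-equivalent then has P(target) 0.536 and P(OD) 0.177, well clear of the limit.

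**How often.** All paths in cohorts of 3 from 100 mg were enumerated under the true curves of Table 10.4.1: 2. Dosing was at q.d. levels, and each path stopped when either 7.1.1 criterion was met at the highest EWOC dose. The table gives the probability that the rule first fires at an untested dose:

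| Scenario | 200 mg b.i.d. evaluated, by 12 | By 42 | q.d. levels only, by 12 | By 42 |
|---|---|---|---|---|
| 1 | 0.07% | 0.82% | 0 | 0.00% |
| 2 | 1.25% | 4.23% | 0 | 0.44% |
| 3 | 0.12% | 1.63% | 0 | 0.00% |
| 4 | 1.45% | 12.23% | 0 | 0.03% |
| 5 | 0.68% | 10.14% | 0 | 0.00% |
| 6 | 0.09% | 0.47% | 0 | 0.37% |

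The planned Part A size is about 12; 42 is the largest trial in Table 10.4.1: 3. Under the simulated rule the probability is 0 by construction.

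**Part B, from the protocol's own table.** In Table 10.4.2: 1, scenarios 7, 8 and 10, the recommended 200/240 has P(target) 0.523, 0.594 and 0.526 and P(OD) 0.057, 0.138 and 0.068. Only 3 of the 9 patients were treated there. Criterion 1 is met at half the simulated minimum of 6, and criterion 2 is not met.

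**The case against.** The strongest reply is that the rule is permissive. The MTD *may* be considered reached, the SMC decides using the model together with other data, and 3.1 and 7.1.1 allow further patients to confirm the estimate. This stands. A reader might infer that the plan would produce an MTD at an untested regimen, but nothing compels that. It is a gap in a guidance rule.

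The 12-patient example is also fragile. Its margin of 0.006 is smaller than the largest difference between the grid and the published posteriors (scenario 5, P(OD): 0.158 against 0.167, a difference of 0.009). A conversion to 305 mg in place of 300 mg gives P(OD) 0.253 and fails EWOC. The 15-patient example is not marginal, but it exceeds the planned size.

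A reader might also infer that such an MTD would have no safety or PK data behind it. That goes too far. In both examples 200 and 400 mg q.d. have been given in this trial and bracket the regimen in the model, and 200 mg b.i.d. has the same total daily dose as 400 mg q.d. Only direct observation of that schedule is missing.

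Finally, it is tempting to ask for the same minimum for the recommended dose, since "it may be any dose which fulfil the escalation with overdose control (EWOC) criterion". But 2.1.1 deliberately lets the SMC set that dose on all available data, including preceding trials. That is a stated design choice, and no passage contradicts it.

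**Conclusion.** The mismatch is plain on the text and does not depend on any calculation: 7.1.1 and 7.1.2 accept either criterion, 10.4.1 and 10.4.2 simulated both conditions together, and the published operating characteristics describe the stricter rule. The consequence that an untested regimen can satisfy criterion 1 is real but uncommon: at most 1.45% by 12 patients, about 12% at the extreme of 42, and at most 0.44% if only q.d. levels are evaluated.

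These frequencies assume cohorts of exactly 3 evaluable patients, an unchanged prior, candidate levels of 50, 100, 200, 300-equivalent and 400 mg, and the MTD taken as the highest EWOC dose. They leave out the 40 and 600 mg levels added for the protocol's simulations, so they are not a rerun of Table 10.4.1: 3. The point is worth correcting, but it does not undermine the dose-finding method.

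**What to change.** Reconcile 7.1.1 and 7.1.2 with 10.4 in one of two ways:

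- attach to criterion 1 the minimum already used in the simulations, 6 evaluable patients at that dose and schedule; or
- keep the rule as written and rerun the operating characteristics under it.

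The first option closes the untested-regimen route. It does not by itself make Table 10.4.1: 3 apply, because criterion 2 would still allow stopping without the 50% condition. The appendix should say so, or the simulations should be rerun in either case.

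In the report, and in the outputs under SAP 7.4.1, label an MTD estimate at a regimen given to no patient as *model-predicted, not tested*.

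The text change is one line per section and one label; a rerun uses the existing simulation set-up. The downside is that in the rare case no MTD is declared, or the confirmatory patients already allowed by 3.1 are used. The rationale for global amendment 4 (protocol 11.4) says that primary endpoint assessment is complete, and SAP section 3 says that Part B was cancelled. For this trial the reporting label and a correct description of the simulated rule are what can still be changed.

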2.1.2 Primary endpoint(s)

- Maximum tolerated dose (MTD).

Proprietary confidential information © 2021 Boehringer Ingelheim International GmbH or one or more of its affiliated companies

- Number of patients with Dose Limiting Toxicities (DLTs) in the MTD evaluation period and thereafter.

A BLRM employing the EWOC principle will be used during the escalation phase for selection of doses and for estimation of the MTD. Cohorts of patients will receive escalating doses of BI 891065 single agent or combination of BI 891065 and BI 754091 until the MTD is reached or the highest planned dose has been tested (see section [4.1.3](#)). Each cohort will consist of newly enrolled patients. Estimation of the MTD will be based upon the estimation of the probability of a DLT in the MTD evaluation period in the set of evaluable patients for MTD (section [3.3.4.1](#)).

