If DLTs are observed in the first two consecutive patients of a previously untested dose level, subsequent enrolment to that cohort will be stopped. The BLMR will re-run to confirm that the dose level still fulfils the EWOC principle. Based on this information, the SMC will evaluate whether the next patients will be enrolled at the same dose level, or if they are enrolled at a lower dose level.

The SMC may decide to stop the dose escalation phase after the criterion for MTD is fulfilled, or the safety in the highest planned dose level is confirmed in the absence of an MTD. Further patients may be included to confirm this MTD estimate, i.e., to confirm that the EWOC criterion is still fulfilled.

The SMC can declare any dose fulfilling the EWOC criterion as RD, independent of the MTD estimate.

In Part B, successive cohorts of patients will receive escalating daily dose of BI 891065 in

Proprietary confidential information © 2021 Boehringer Ingelheim International GmbH or one or more of its affiliated companies

combination with a fixed dose of BI 754091 at 240 mg once every 3 weeks. The planned starting dose of BI 891065 in Part B is 200 mg, and this cohort will commence after the safety of the same dose level in Part A is confirmed. Other doses may be investigated depending on the safety data obtained from Part A and from the preceding first-in-human trial (1379-0001). SMC will make the decision based on recommendation from BLRM as well as other safety information. BLRM with overdose control will be implemented in Part B incorporating all available information of BI 891065 and BI 754091 to quantify the probability of observing a DLT once patient information becomes available.

The dose escalation will continue until any of the following occurs:

1. the MTD is reached
2. the safety in the highest planned dose level (400 mg) is confirmed
3. the safety at the highest dose tolerated in Part A is confirmed (applicable when this dose is less than 400 mg).

In Part B the dose escalation will follow the approach as described for Part A.

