10.4.1 Part A

Hypothetical data scenarios:

Hypothetical data scenarios are shown in Table [10.4.1: 1](#). These scenarios reflect potential on-study data constellations and related escalation as allowed by the model and the 100% escalation limit. It is assumed that each cohort has exactly three patients who are all evaluable. For each scenario, the probability of overdose for the current dose, as well as the next potential dose and related probabilities of under-dosing, target dose, and over-dosing are shown.

For example, scenario 1 represents the case that no DLT is observed in the first three patients at the starting dose of 100 mg. In this case, the next optimal dose, i.e. the dose with the highest probability of being in the target interval, is 400 mg. Since the escalation is restricted to a maximum of 100 % from the previous dose per protocol, the next dose to be tested in the trial would be 200 mg. Similarly, scenario 4 represents the case that 3 patients have been treated at 100 mg and 3 at 200 mg, none of them with a DLT. In this case, the model requires to escalate to 400 mg.

Scenario 3 shows the case that 2 DLTs are observed in the first three patients at the starting dose of 100 mg. The model then allows the next dose to be de-escalated to 50 mg.

Finally, scenario 8, 9 and 10 illustrate a case where escalation has proceeded up to the highest dose of 400 mg, where the MTD could be declared at 400 mg.

Table 10.4.1: 1 Hypothetical data scenarios

Scenario	Dose (q.d. mg)	# Patients	# DLT	Current Dose: P (OD)	Next recommended dose	Next dose:		
						P (UD)	P (TD)	P (OD)
1	100	3	0	0.001	400*[200]	0.834	0.106	0.060
2	100	3	1	0.041	400*[200]	0.564	0.253	0.184
3	100	3	2	0.316	50	0.533	0.262	0.205
4	100	3	0					
	200	3	0	0.002	400	0.871	0.091	0.039
5	100	3	0					
	200	3	1	0.030	400	0.596	0.237	0.167
6	100	3	0					
	200	3	2	0.193	200	0.479	0.327	0.193
7	100	3	1					
	200	3	1	0.140	200	0.520	0.340	0.140
8	100	3	0					
	200	3	0					
	400	6	0	0.001	400	0.970	0.029	0.001
9	100	3	0					
	200	3	0					
	400	6	1	0.023	400	0.814	0.163	0.023
10	100	3	0					
	200	3	0					
	400	6	2	0.134	400	0.496	0.371	0.134
11	100	3	0					
	200	3	0					
	400	6	3	0.413	200	0.824	0.164	0.013
12	100	3	0					
	200	3	0					
	400	6	4	0.745	200	0.763	0.198	0.039

Operating characteristics:

Operating characteristics are a way to assess the long-run behaviour of a model by illustrating the precision of the design in estimating the MTD. Under an assumed true dose-toxicity curve,

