5. ENDPOINTS(S)

5.1 PRIMARY ENDPOINT(S)

Part A:

The primary endpoints for Part A of the trial are:

- Maximum tolerated dose (MTD)
- the number of patients with dose-limiting toxicities (DLTs) during the MTD evaluation period (first treatment cycle).

For definition of the MTD, refer to Section 2.1.1 of the CTP.

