7.4 PRIMARY ENDPOINT(S)

7.4.1 Primary analysis of the primary endpoint(s)

The primary endpoints of Part A are the MTD of BI 891065 and the number of patients with DLTs in the first treatment cycle. The number of patients with DLTs at each dose level will be presented for the first cycle for the MTD evaluation set and for the whole on-treatment period for the treated set separately.

The MTD will be determined by the SMC using recommendations from a Bayesian logistic regression model (BLRM, see CTP Section 7 for details on the model and on the prior). BLM evaluations for the CTR will be performed once using the number of patients with DLTs during the first cycle from the MTD evaluation set and once using the number of patients with DLTs during the whole on-treatment period from the treated set.

Tables and bar charts displaying the posterior probabilities of the true DLT rates being in either the underdosing interval, the targeted toxicity interval or the over toxicity interval will be produced.

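### Does the 12/6 count criterion leave the MTD label open when 400 mg is free of DLTs, and does it count the wrong patients?

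*Protocol*

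**What the plan says.** Protocol 2.1.1 defines the MTD as "the highest dose with less than 25% risk of the true DLT rate being equal or above 33" per cent in the first cycle. That is a ceiling on overdose risk; it does not require the dose to be toxic.

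Protocol 7.1.1 gives two permissive routes to an MTD in Part A. One is a posterior probability above 0.5 that the DLT rate lies in the target interval. The other is "At least 12 patients have been treated in the dose escalation phase of the trial, of which at least 6 at the MTD". Part B (7.1.2) has the same structure with 9 in place of 12.

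Protocol 3.1 lets the SMC stop escalation once the MTD criterion is met, or if "the safety in the highest planned dose level is confirmed in the absence of an MTD". Appendix 10.4.1 describes Scenarios 8 to 10 as a case "where the MTD could be declared at 400 mg"; Scenario 8 has no DLT in 12 patients.

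SAP 5.1 adds no definition of its own: "For definition of the MTD, refer to Section 2.1.1 of the CTP". SAP 7.4.1 states "The MTD will be determined by the SMC using recommendations from a Bayesian logistic regression model" and promises "Tables and bar charts displaying the posterior probabilities of the true DLT rates" for the three toxicity intervals, together with DLT counts by dose.

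On the population, Protocol 2.1.2 bases MTD estimation on DLT probability "in the set of evaluable patients for MTD". Protocol 7.3 restricts MTD determination to MTD-evaluable patients, and Protocol 7.3.1.1 and SAP 6.3 agree.

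**The concern.** The MTD is a primary endpoint. A trial that runs to its planned size with no DLT at the cap could report 400 mg as the MTD, or report that no MTD was found and the highest planned dose was tolerated. A reader may take the first as a toxicity limit and the second as the absence of one, although the data are the same. Neither document states which label comes first, and the SAP refers the question back to the protocol and to the SMC.

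The count also says *treated*. If some of six treated patients at 400 mg were not evaluable for DLT, the criterion could be met on less information than it appears to require.

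**Working it through.** **Inputs.** The model is logit(π_d) = log α + β·log(d/200) (Protocol 7.1.1). The prior for (log α, log β) is the mixture in Table 7.1.1: 2: weight 0.9 on means (−3.66, −0.28), SDs (1.20, 0.83), correlation −0.10; weight 0.1 on means (−3, 0), SDs (2, 1), correlation 0. The posterior is proportional to the prior times the product of π_d^x·(1−π_d)^(n−x) over doses, integrated on a grid. UD, TD and OD are the probabilities of π_d in [0, 0.16), [0.16, 0.33) and [0.33, 1]. Overdose control (EWOC) requires P(OD) < 0.25.

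**Step 1. Reproduce the protocol's figures (UD/TD/OD).**

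| Case | Grid | Protocol |
|---|---|---|
| Prior, 400 mg | 0.811/0.115/0.074 | 0.813/0.115/0.072 |
| Prior, 200 mg b.i.d. modelled as 300 mg | 0.872/0.086/0.042 | 0.873/0.086/0.041 |
| Scenario 8 (0/3, 0/3, 0/6), 400 mg | 0.970/0.028/0.002 | 0.970/0.029/0.001 |

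**Step 2. Is the count the only route at a DLT-free cap?** The shortest path is 3 + 3 + 6 = 12 patients, which is the planned Part A size. In Scenario 8, P(TD) = 0.028, far below 0.5. More DLT-free patients at 400 mg lower it further: 0.009 at 0/12 and 0.001 at 0/24. So yes.

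**Step 3. Use this trial's own data.** Table 7.1.2: 1 records 1/3 DLTs at 100 mg. The 0/3 at 200 mg and 0/6 at the top dose are assumptions.

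| Top dose and prior | UD | TD | OD |
|---|---|---|---|
| 400 mg q.d., Table 7.1.1: 2 prior | 0.896 | 0.098 | 0.006 |
| 200 mg b.i.d. as 300 mg, same prior | 0.919 | 0.077 | 0.004 |
| 400 mg q.d., Table 7.1.2: 4 BI 891065 prior (illustration; already contains the 1/3) | 0.661 | 0.319 | 0.020 |

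P(TD) is at most 0.319, so only the count is met. P(OD) is at most 0.020 against the limit of 0.25. The cap is the highest planned dose and satisfies EWOC, so calling it the MTD agrees with 2.1.1. Saying that no toxicity limit was found agrees with 3.1.

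**Step 4. Would a fixed label for the zero-DLT case help?** Continue from 1/3 at 100 mg and 0/3 at 200 mg, with the Table 7.1.1: 2 prior. At 400 mg, 1/6 gives 0.668/0.289/0.043 and 2/6 gives 0.368/0.467/0.165. Both fail P(TD) > 0.5, satisfy EWOC and qualify only by count. A rule for zero DLTs leaves these untouched. It would also produce a *not reached* label by chance when the true rate at the cap is at or near the target range: P(0/6) = 0.84^6 = 0.351 at 16%, 0.75^6 = 0.178 at 25%, and 0.67^6 = 0.090 at 33%.

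**Step 5. Treated against evaluable.** Protocol 3.3.4.1 requires replacement when fewer than two patients in a cohort are evaluable. It also permits replacement after a missed cycle 1 visit that makes a patient non-evaluable, and 3.1 lets the SMC enrol more patients. Two cohorts of three at 400 mg could still leave 6 treated and 4 evaluable. After 1/3 and 0/3, 0/4 at 400 mg gives 0.854/0.132/0.014, against 0.896/0.098/0.006 for 0/6. EWOC holds in both.

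**The case for a change.** The strongest case for a change is that both labels are already in use for DLT-free top doses. Protocol 4.1.2.1 says the MTD was not reached in the preceding trial, which had 0/6 at 400 mg, while Appendix 10.4.1 would allow an MTD of 400 mg in Scenario 8. Reaching the planned 12 patients can trigger the overlap, so it is not remote. The simulations required both six evaluated patients and a target probability of at least 50%, so they do not assess the count route. A one-sentence precedence rule would cost little.

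The overlap is real, and the remark about the simulations is correct, though it concerns the operating characteristics and not the label. The rest does not carry. The no-MTD branch in 3.1 is worded as a residual case, so the natural order is to check the MTD criterion first. What remains is SMC discretion, which is usual in a model-guided phase I design. Imposing a *not reached* label on data that satisfy 2.1.1 and 7.1.1 would contradict Scenario 8. It would also fix a primary-endpoint label after the interim database lock of 29 March 2021, by which time Amendment 4 (Protocol 11.4) says the primary endpoint assessments were complete.

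On the second part, *treated* is loose wording, and a strict evaluable count could fall short of six. But Protocol 7.3 is categorical about the population, and three other sections agree with it.

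**Conclusion.** No change is needed. The labelling question is an overlap between two permitted descriptions, neither of which is wrong under the protocol's definition. The reader of the report is protected because SAP 7.4.1 puts the DLT counts and the three interval posteriors beside whichever label the SMC uses; 0/6 with a high under-toxicity probability would be plain to see. Escalation, overdose control and the recommended dose are the same either way, since the SMC may declare any dose meeting EWOC as the recommended dose.

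The word *treated* is a clerical slip that an analyst resolves from Protocol 7.3, 7.3.1.1 and SAP 6.3. Its numerical effect in the case examined is a shift in P(OD) from 0.006 to 0.014. The matching wording in Part B has no consequence, because SAP 3 records that Part B was cancelled.

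These sizes rest on the assumed 0/3 at 200 mg and no DLT at the top dose; the documents report only 1/3 at 100 mg for this trial. They also depend on the prior, which the protocol allows to be updated. Under both priors tried, a DLT-free cap meets EWOC comfortably and fails the 0.5 target criterion, so the conclusion does not turn on that choice.
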